**Figure 3 Overview of End of Treatment Period**

### **3.1.4 Follow-up Period**

[figure not shown]
Patients who discontinue treatment early will be followed up for at least 96 weeks after the Early Treatment Discontinuation Visit. Patients who complete the 96 weeks Treatment Period and, in agreement with their treating neurologist, decide not to continue in a separate LTE study, will be followed up for at least 96 weeks after the end of the Treatment Period.

Patients who decide to leave the study and switch to commercially marketed Ocrelizumab, either after completion of the 96 weeks Treatment Period or after early discontinuation of the 96 weeks Treatment Period, will not enter the safety Follow-up Period.

Any patient whose peripheral blood B-cell count remains depleted after this period will continue to be monitored at 24-week intervals until the B-cell count has returned to the baseline value or to lower limit of normal (LLN) range, whichever is lower.

[Figure 4](#) provides an overview of the Follow-up Period, which is the variable B-cell monitoring period. A schedule of assessments for the Follow-up Period is presented in [Appendix 2](#).

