**Figure 4 Follow-up: Variable B-Cell Monitoring Period**

During the Follow-up Period, patients will be formally assessed at clinical visits every 24 weeks and by telephone contacts every 8 weeks. If further B-cell monitoring is required and the patient is not receiving any other B-cell targeted therapy, assessments will take place at clinical visits every 24 weeks and by telephone contacts every 8 weeks until the B-cells are repleted. See [Appendix 2](#) for further details.

After initiation of study drug, all adverse events will be reported until 96 weeks after the end of the Treatment Period but may be extended in patients whose B-cells take longer to replete.

Related SAEs must be collected and reported regardless of the time elapsed from the last study drug administration, even if the study has been closed.

For patients withdrawing from treatment early, every effort should be made to complete the Follow-up Period and all related assessments regardless of whether or not they receive alternative treatment for MS.

A dedicated (scheduled or unscheduled) follow-up clinic visit directly prior to the start of an alternative MS treatment is required in order to assess the patient's clinical status and safety parameters (assessments to be performed as per [Appendix 2](#), Schedule of Assessments: Follow-up including further B-cell monitoring period).

Patients who receive alternative MS therapies that may decrease B-cell levels will only be followed up for 96 weeks; they will not be entered into the prolonged B-cell Monitoring period thereafter.

A structured telephone interview will be conducted by site personnel every 8 weeks between the study visits during the treatment period and follow-up to identify and collect information on any changes in the patient's health status that warrant an unscheduled

visit (including new or worsening neurological symptoms) and possible events or infections.

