### **5.3.1 Adverse Event Reporting Period**

Investigators will seek information on adverse events at each patient contact. All adverse events, whether reported by the patient or noted by study personnel, will be recorded in the patient's medical record and on the Adverse Event eCRF.

**After informed consent has been obtained but prior to initiation of study drug**, only serious adverse events caused by a protocol-mandated intervention (e.g., invasive

procedures such as biopsies, discontinuation of medications) should be reported (see Section 5.4.2 for instructions for reporting serious adverse events).

**After initiation of study drug**, all adverse events will be reported until 96 weeks after the end of the Treatment Period, but may be extended in patients whose B-cells take longer to replete.

Related SAEs must be collected and reported regardless of the time elapsed from the last study drug administration, even if the study has been closed.

Instructions for reporting adverse events that occur after the adverse event reporting period are provided in Section 5.6.

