This study is a prospective, multicenter, open-label, efficacy and safety study in patients with RRMS who have had a suboptimal response to an adequate course of a DMT. An adequate course of prior DMT is defined as a stable dose of the same DMT administered for at least 6 months. The first dose of ocrelizumab will be administered as an initial dose of two 300-mg infusions (600 mg total) in 250 mL 0.9% sodium chloride each separated by 14 days (i.e., Days 1 and 15) followed by one 600-mg infusion in 500 mL 0.9% sodium chloride every 24 weeks for the remainder of the study duration.

This study will enroll approximately 750 patients. Patients will be assessed for efficacy and safety every 24 weeks as described in the Schedule of Assessments in [Appendix 2](#).

The study will consist of the following periods:

- Screening period: Up to 4 weeks
- Treatment period: Open-label treatment period of 96 weeks (last dose administered at Week 72)
- A follow-up period of at least 2 years, which is independent of the DMT administered

Follow-up Period: Patients who discontinue treatment early will be followed up for at least 96 weeks after the Early Treatment Discontinuation Visit. Patients who complete the 96 weeks Treatment Period and, in agreement with their treating neurologist, decide not to continue in a separate long term extension (LTE) study, will be followed up for at least 96 weeks after the end of the Treatment Period. Patients who decide to leave the study and switch to commercially marketed ocrelizumab, either after completion of the 96 weeks Treatment Period or after early discontinuation of the 96 weeks Treatment Period, will not enter the safety Follow-up Period.

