4.6.2 Adverse Events

For each recorded adverse event (AE), the term entered by the investigator describing the event (the “reported term”) will be assigned a standardized term (the “Preferred Term” [PT]) and assigned to a superclass term (the “System Organ Class” [SOC]) on the basis of the MedDRA World Health Organization (WHO) dictionary of terms.

Treatment emergent adverse events (TEAEs) will be summarized by SOC and PT. At each level of summarization (at least one event, SOC and PT), patients reporting more than one AE will be counted only once. For TEAEs by grade (intensity), the highest grade

will be reported. The table results will be sorted by descending frequency of SOC and PT within each SOC.

Summary of TEAEs will be repeated for the following subgroups, provided that they include at least 50 patients:

- Last DMT prior to study enrolment
 - Interferons (Interferon β 1a, Interferon β 1b, Peg Interferon β 1a)
 - Glatiramer acetate
 - Teriflunomide
 - Fingolimod
 - Dimethyl fumarate
 - Natalizumab

Definitions

Treatment-emergent adverse events (TEAE): AEs with an observed or imputed date of onset on or after the start date of trial treatment. If the onset date of the AE is prior to the day of first dose, the AE will be considered treatment-emergent only if the most extreme intensity is greater than the initial intensity (i.e., the intensity for a given AE increases and its end date is on or after the date of the first dose). An AE with a completely missing, non-imputed start date will be assumed to be treatment emergent unless the AE has a complete, non-imputed end date that is prior to the date of the first dose.

An adverse event will be considered as treatment-emergent in the period “baseline to week 24”, if the AE onset date occurred on or after the start date of trial treatment and before start date of trial treatment + 24 weeks. An adverse event will be considered as treatment-emergent in period “>= week X – week Y”, if the AE onset date occurred on or after the start date of trial treatment + week X and before start date of trial treatment + Y weeks. If the emergence of an AE cannot be clearly assigned to a period, the AE will be considered emergent across all appropriate periods.

Imputation of incomplete date: in order to evaluate if an AE is treatment-emergent, incomplete dates will be imputed as follows:

- If the start date is incomplete:
 - If the day is missing, impute to 01
 - If the day and months are missing, impute to 01JAN

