 - If the date is completely missing, it is considered treatment-emergent
- If the end date is incomplete:
 - If the day is missing, impute to the last day of the month
 - If the day and month are missing, impute to 31DEC
 - If the date is completely missing, it is considered treatment emergent

Serious Adverse events (SAEs): all SAEs including serious MS relapses and serious Infusion Related Reactions (IRRs).

Dose assigned to an AE: only applicable if the AE onset date is on or after the date of the first infusion of that dose but before the first infusion of the next treatment dose. AEs that are reported during the safety follow-up period will be assigned to the last dose received. AEs that start prior to the first dose and worsen during treatment (i.e., treatment-emergent) will be assigned to the first treatment dose.

Output Conventions

All analyses of AE data will be performed using the PTs unless otherwise specified.

For all summary tables, the AEs will be sorted by SOC (in decreasing order of overall incidence) and then by PT (in decreasing order of overall incidence). All summaries and listings of AEs will be based on the ITT population. Summaries of AEs will be generated to summarize the incidence of treatment-emergent AEs only (TEAE and AE are used exchangeable).

A listing of all AEs will be provided, including all relevant information (including -but not limited to- start date, end date and the corresponding study days, related to treatment, seriousness, Grade, treatment-emergence).

Incidence Analysis on number of the events and number of patients with at least one event:

Overview of TEAE, including

- AE
- Serious AE
- Death
- AE with fatal outcome
- Infusion related reaction (IRR)
- Serious infusion related reaction (IRR)
- Infections (using the MedDRA SOC of “Infections and Infestations.”)
- Serious infection (using the MedDRA SOC of “Infections and Infestations.”)
- AE leading to study drug discontinuation (“Drug Withdrawn” for the “Action taken with ocrelizumab due to SAE/AE” field in the “Adverse Event/IRR/MS Relapse” eCRF form)
- Serious AE leading to study drug discontinuation (“Drug Withdrawn” for the “Action taken with ocrelizumab due to SAE/AE” field in the “Adverse Event/IRR/MS Relapse” eCRF form)
- AE leading to dose modification/interruption
- Serious AE leading to dose modification/interruption

- AE related to study medication,
- AE of Grade ≥ 3

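### Treatment-emergent AEs have a start date but no end date, so the crude incidence tables pool unequal observation windows, some of them on another MS drug

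*SAP*

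**What the plan says.** The definition in SAP 4.6.2 has a lower bound only: "AEs with an observed or imputed date of onset on or after the start date of trial treatment". The dose rule in the same section brings later events into scope: "AEs that are reported during the safety follow-up period will be assigned to the last dose received". AE summary tables are limited to treatment-emergent events in the ITT population. Each patient is counted once per level, and the TEAE summary is repeated by last prior DMT. SAP 2.4 confines the efficacy analysis to the Treatment Period but sets no such limit for safety. Protocol 6.5.2 gives no end date either.

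How long a patient is observed depends on how the patient leaves:

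- Completers who decline the extension "will be followed up for at least 96 weeks after the end of the Treatment Period".
- Early stoppers: "Patients who discontinue treatment early will be followed up for at least 96 weeks after the Early Treatment Discontinuation Visit".
- Patients who switch to commercial ocrelizumab "will not enter the safety Follow-up Period" (Protocol 3.1.4). Completers who roll into the extension are not followed in this study either.
- For patients who stop treatment early, Protocol 3.1.4 wants follow-up completed "regardless of whether or not they receive alternative treatment for MS".
- The reporting period "may be extended in patients whose B-cells take longer to replete" (Protocol 5.3.1).

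**The concern.** A crude percentage of patients with an event has a clear meaning only if everyone is observed over a comparable window. Here the window is set by the exit route. The headline percentages for any TEAE, for SOC and PT, for serious events and for Grade 3 or higher would therefore depend partly on how many patients decline the extension and on when the database is cut. An event that starts on a later DMT still meets the definition and is tied to an ocrelizumab dose. The last-DMT subgroup tables inherit the same mixture. So does the table of common non-serious TEAEs that the SAP marks for the public registries, where a 5% threshold decides what is shown.

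**Working it through.** **Period lengths.** Screening is 4 weeks, enrolment about 12 months (52 weeks), treatment 96 weeks and follow-up at least 96 weeks (Protocol 3.1 and 3.2). The sum is 4 + 52 + 96 + 96 = 248 weeks, or 4.75 years. This reproduces the protocol's approximate 5 years.

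**Window ratio, completers who enter follow-up against completers who leave at Week 96.**
- Follow-up complete: (96 + 96)/96 = 2.0. This is a floor.
- Longest repletion time quoted in Protocol 5.1.1.1: 175 weeks after the Week 72 dose is Week 247. The next 24-weekly visit is Week 264, and 264/96 = 2.75.
- Primary cut-off, assumed to fall 24 weeks after the last patient's Week 96 visit, with 52 weeks of enrolment. Last enrolled: (96 + 24)/96 = 1.25. First enrolled: (96 + 24 + 52)/96 = 1.79.

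**Early stoppers who enter follow-up, against patients who stop at the same time and switch to commercial drug.** Stop at Week 24: (24 + 96)/24 = 5.0. Week 48: 144/48 = 3.0. Week 72: 168/72 = 2.3.

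**Effect on an incidence percentage (illustration).** Protocol 1.2 reports infections in 58.4% of ocrelizumab patients over 96 weeks, with 1224 events. Let f be the share of patients who complete 96 weeks of follow-up. The documents do not give f, so 10, 20 and 30% are assumed. The pooled value is (1 − f) × 58.4% + f × P(192 weeks).

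- *One constant hazard for all.* P(192) = 1 − (1 − 0.584)² = 82.7%. Pooled: 60.8, 63.3, 65.7%.
- *Allowing for clustering.* The protocol does not give the group size in that passage, but 4 patients are reported as 0.5%, so N lies between 4/0.0055 = 727 and 4/0.0045 = 889. The mean is then 1224/N = 1.68 to 1.38 events per patient. A Poisson count with 58.4% affected would have a mean of −ln(0.416) = 0.88, so events cluster within patients. For a negative binomial with mean m and shape k, solving (1 + m/k)^(−k) = 0.416 gives k = 0.74 to 1.04. Then P(192) = 1 − (1 + 2m/k)^(−k) = 71.8 to 74.0%. Pooled: 59.7–60.0, 61.1–61.5 and 62.4–63.1%, that is, about 60, 61 and 63%.

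**Rate denominators.** SAP 4.6.2 divides by total time in the study. In SAP 4.6.1, treatment duration runs to last contact, death or the cut-off, so time off drug counts. Infusion-related reactions arise during or within 24 hours of an infusion (Protocol 5.3.5.1) and cannot accrue in follow-up. If 20% of patients complete 96 weeks of follow-up, and everyone otherwise contributes 96 weeks, person-time rises by a factor of 1.2. Their rate then falls by 1 − 1/1.2 = 17%.

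**The case against.** The SAP already has several safeguards:

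- Rates per 100 patient-years are planned for infections, serious infections, fatal, related and Grade 3 or higher events, and infusion reactions.
- Epoch tables stop at Week 96.
- Related TEAEs have their own tables, and the listing carries study day.
- SAP 2.4 places a follow-up update in a CSR addendum, with listings only where fewer than 50 patients have data.
- The cut-off date and the AE collection period bound the window in practice.

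An open window is also defensible in part. Median B-cell repletion was 72 weeks, with a range of 27 to 175, so late events may be delayed harm. The study is single-arm and descriptive.

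Most of this stands, but it leaves gaps. Overall AEs and overall SAEs are missing from the rate list. No table gives cumulative incidence over the Treatment Period. The epoch tables run on time since first dose, so an early stopper's event on a new DMT before Week 96 still counts. SAP 2.4 includes all data before the cut-off in the primary analysis, and nothing there removes follow-up AEs from the TEAE tables.

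A reader might go further and infer four things that the documents do not support:

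- *The window is at most doubled.* Follow-up is a minimum and can be extended, so two is the completer's floor after full follow-up. At the primary cut-off the ratio is lower.
- *Infections would reach 82.7% in followed patients.* That needs one hazard shared by all, which the protocol's own event count contradicts.
- *Subgroup comparisons are biased.* Nothing shows that entry to follow-up differs by last DMT.
- *Late events should be dropped as unrelated.* Slow B-cell return argues against that.

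**Conclusion.** The point holds as a worthwhile, inexpensive correction to the safety tables. The gap lies in the wording of the definition and does not depend on any calculation. Collecting late AEs is sound. The problem is pooling them in crude percentages with patients whose observation ended at Week 96.

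The likely shift is modest. For infections it is about 1 to 5 percentage points with clustering and 2 to 7 under one constant hazard, for an assumed 10 to 30% completing follow-up. These figures describe the position once follow-up is complete. They also assume that the event rate in follow-up equals the on-treatment rate and that every other patient has 96 weeks. The window ratios of 1.25 to 1.8 at the primary cut-off rest on the assumed enrolment span and cut-off date.

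**What to change.** In SAP 4.6.2:

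1. Produce the main TEAE incidence tables, including the last-DMT subgroup tables, for AEs with onset in the Treatment Period. Give early stoppers an explicit end date tied to treatment discontinuation. SAP 2.4 ends the period at a withdrawal date that 4.4.2.2 says is defined in 4.6.1, but 4.6.1 defines only last contact.
2. Report AEs with onset in safety follow-up in a separate table with its own person-time. Flag those that start on or after the first use of another DMT, and keep them visible there and in the full listing.
3. Add overall AE and overall SAE rates per 100 patient-years, and match each rate's denominator to its window. Cutting the numerator alone would bias the rates downward.

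The cost is SAP wording and an extra set of table runs. No new data are needed, since SAP 4.2 already summarises DMT use after ocrelizumab. The downside is that late AEs leave the headline table, though they remain in their own table and in the listing.

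### Partial AE start dates are set to day 01 or 01JAN with no first-dose exception, so some new post-dose AEs drop out of the overall TEAE tables (minor)

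*SAP*

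**What the plan says.** All the rules are in SAP 4.6.2 Adverse Events.

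- **Purpose of the imputation:** "in order to evaluate if an AE is treatment-emergent, incomplete dates will be imputed as follows".
- **Start date, day missing:** "If the day is missing, impute to 01".
- **Start date, day and month missing:** "If the day and months are missing, impute to 01JAN".
- **Start date wholly missing:** "If the date is completely missing, it is considered treatment-emergent".
- **TEAE definition:** "AEs with an observed or imputed date of onset on or after the start date of trial treatment". An imputed onset has the same force as an observed one.
- **Onset before first dose:** "the AE will be considered treatment-emergent only if the most extreme intensity is greater than the initial intensity".
- **Tables:** "Summaries of AEs will be generated to summarize the incidence of treatment-emergent AEs only". A separate listing covers all AEs, with a treatment-emergence flag, and SAEs and deaths are also listed.
- **Epochs:** after defining the time periods, the SAP adds "If the emergence of an AE cannot be clearly assigned to a period, the AE will be considered emergent across all appropriate periods".

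No clause compares the imputed start with the first-dose date. Protocol 6.5.2 asks for all AEs on or after Day 1 treatment to be summarized, but SAP section 4 states that the SAP takes precedence over the protocol, so that text does not repair the rule.

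**The concern.** The imputed date can fall before first dose when the true onset was after it. The only way back into the TEAE tables is then an increase in grade; a post-dose end date does not help an AE of constant grade.

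Two features make this hard to defend. First, it is inconsistent: knowing only that the AE began in March removes it, while knowing nothing about the start keeps it. Second, it takes the less likely side. Under Protocol 5.3.1 and 5.4.2.1 the only AEs reported before first dose are SAEs caused by a protocol-mandated intervention, so a new AE dated to the first-dose month probably began after dosing.

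At stake are the overall TEAE counts (all, serious, related, Grade 3 or higher) in a single-arm study whose safety endpoints include the rate of AEs.

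**Working it through.** The documents give no figure on this point, so there is none to reproduce.

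**Worked case under the SAP rules.** First dose 15 March 2017, true onset 20 March, constant grade.

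| Start date recorded | Date used | TEAE? |
|---|---|---|
| 20 March 2017 | 20 March | yes |
| March 2017 | 1 March | no, even with an end date of 5 April |
| 2017 | 1 January | no |
| none | none | yes |
| March 2017, grade increases | 1 March | yes |

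One exception: if the end date is wholly missing and the last end-date bullet is read literally, the AE is kept as treatment-emergent.

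**Inputs.** Treatment period 96 × 7 = 672 days (SAP section 2). Assumptions: 365-day year, first-dose dates spread evenly over it, onsets spread evenly over the 672 days, constant grade.

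**Missing day.** In a month of length L, a first dose on day d loses onsets from d to L, except when d = 1. The loss summed over the month is L(L−1)/2.
- Sum over the year: 7×465 + 4×435 + 378 = 5,373.
- Mean window: 5,373/365 = 14.7 days; 14.72/672 = 2.2% of onsets.
- Among post-dose onsets in the first-dose calendar month, 93.6% are classed as pre-dose.

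**Missing day and month.** Mean window (365−1)/2 = 182 days; 182/672 = 27.1% of onsets.

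**Loss per 1,000 post-dose AEs** = 1000 × (0.0219p + 0.2708q), where p is the share lacking the day and q the share lacking day and month. The documents give neither, so the values below are assumptions.

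| p | q | Lost per 1,000 |
|---|---|---|
| 1% | 0% | 0.2 |
| 5% | 0.5% | 2.4 |
| 10% | 0% | 2.2 |
| 10% | 2% | 7.6 |

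Of the 7.6, 5.4 comes from q alone.

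**Epoch check.** Mean days of onset assigned to each period, over all 365 first-dose dates and onset days 0 to 671. The true values are 168 / 168 / 336.

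| Rule | Baseline to week 24, day missing | Baseline to week 24, day and month missing |
|---|---|---|
| SAP rule as it stands | 168.0 (loses 14.7, gains 14.7) | 168.0 (loses 129.1, gains 129.1) |
| Later of imputed and first-dose date, also used for epochs | 182.7 | 350.0 |
| Count in every period the known month or year overlaps | 182.7 | 350.0 |

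The last option also duplicates events in later periods: 182.7 / 197.4 / 350.7 with the day missing, and 350.0 / 478.0 / 516.9 with day and month missing. The latter counts about 1,345 days for 672 true days.

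**After the fix.** Over the same grid, no post-dose onset is lost from the overall TEAE count in either case.

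**The case against.** **The sentence on unclear periods already covers this.** It closes the paragraph that defines the time periods and settles which period an AE belongs to. The imputation rule comes after it and is stated to decide emergence itself. A bullet under All TEAEs in the same section breaks off mid-sentence; it appears to concern allocation to periods, but its content is missing and cannot be shown to help.

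**The reach is small.** This stands. An event is lost only if its date is partial, its onset falls in the month or year of first dose, its grade does not rise and, on the literal reading above, it has an end date. Partial dates are unlikely for SAEs (24-hour reporting, Protocol 5.4) and for infusion-related reactions (tied to an infusion, Protocol 5.3.5.1). AEs are assessed at baseline and Week 2 (Protocol Appendix 1). Data queries, source data verification, 8-weekly calls and optional diaries all reduce partial dates. No between-arm contrast can be distorted.

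**The percentages lean high.** Also fair. AEs are reported until 96 weeks after the Treatment Period (Protocol 5.3.1), and the TEAE definition has no end date. For a patient followed that far, with onsets spread evenly over 672 + 672 = 1,344 days, the shares halve to 14.7/1,344 = 1.1% and 182/1,344 = 13.5%.

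**Events are not patients.** The SOC and PT tables count a patient once per level, so incidence changes only if the dropped AE was that patient's sole qualifying event at that level.

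A reader might go further and infer that these events vanish from the report, or that the first epoch is understated. Neither follows. They stay in the all-AE listing, and in the SAE or death listing if serious or fatal. In the first epoch, back-dating loses and gains equally under the stated assumptions.

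**Conclusion.** The rule gives a wrong result as written: a post-dose AE of constant grade dated only to the first-dose month or year is excluded from the overall TEAE tables, while less date information would have kept it. For truly post-dose events the bias in those tables runs only towards undercounting, and nothing else in the documents removes it.

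It is a minor point. The mean windows of 14.7 and 182 days rest on even spreads of first-dose dates and onsets. Any count of lost events rests on partial-date rates that the documents do not state. A claim of material under-reporting of safety is not supported, and no net effect is claimed for the baseline to week 24 epoch.

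**What to change.** Add one or two sentences to the imputation rules in SAP 4.6.2: if the known part of the start date is compatible with onset on or after first dose, and the observed or imputed end date is not before first dose (or is wholly missing), set the start to the later of day 01 (or 01JAN) and the first-dose date. Use that date to decide overall treatment emergence. Otherwise keep the current rule.

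Limit the change to overall TEAE status, and state that rescued, partially dated AEs will slightly inflate baseline to week 24. Applying the existing sentence on unclear periods does not avoid this: it gives the same first-epoch totals and adds duplicates later.

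The cost is a small programming change. TEAE counts may rise slightly, and a few truly pre-dose AEs with partial dates may be counted as treatment-emergent; the end-date condition limits these.
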